In addition to poor quality of life, dyspnea is linked to increased pain, anxiety, and mood disturbance among patients with cancer. In a cohort of 120 patients with early and late-stage lung cancers, approximately 87% reported experiencing dyspnea, and those with more severe symptoms also had worse pain and anxiety.²⁷ For some individuals, dyspnea is associated with feelings of panic and impending death.⁸ We found in our own investigation of patients with lung cancer that those with dyspnea were twice as likely to have panic attacks compared to those without respiratory symptoms.²⁸ Furthermore, investigators have observed that dyspnea is related to depression, anxiety, fatigue, cough, and decreased coping capacity in patients with cancer receiving palliative care services.²⁹ These studies underscore that the experience of dyspnea is multifaceted, involving physical and psychological factors, and requires comprehensive symptom assessment and management.

Dyspnea is Associated with Increased Service Utilization

Compounding the suffering experienced by patients and families, dyspnea is a major cause of healthcare utilization among individuals with cancer. Specifically, respiratory distress accounted for the greatest number of emergency department (ED) visits in patients with lung cancer (32% of visits) in one study of cancer-related ED utilization. Many of these patients were subsequently admitted to the hospital after ED evaluation.¹³ This trend persists throughout the course of disease, as dyspnea is the second most common reason for visits to the ED in the final two weeks of life for patients with cancer.¹² Data suggest that the median survival for patients with lung cancer who present to the ED with dyspnea is only four weeks.³⁰ In the ambulatory care setting, one study showed that over half of patients with lung cancer (57%) utilized many services across disciplines, such as pulmonary rehabilitation and physical therapy, given their high symptom burden.³¹ Thus, the Quality Oncology Practice Initiative of

the American Society of Clinical Oncology has identified the assessment and management of dyspnea as a key measure of quality cancer care.¹⁴

Novel Treatment Approaches for Dyspnea Are Greatly Needed

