[name] recently completed a pilot study to evaluate the feasibility of using actigraphy to measure performance status in 42 patients with metastatic NSCLC. Participants wore wrist actigraphs for three days prior to completing questionnaires assessing symptoms, including dyspnea, and their activity level. Eastern Cooperative Oncology Group performance status (ECOG PS) has a clinically meaningful difference in scores based on whether a patient is inactive for at least half the time they are awake. Actigraphy objectively captures the percentage of time a person is immobile but awake. Actigraph reports of participants' percent time spent immobile but awake ranged from 4-50% (Mean=18%, SD=11%). Percent of time awake and spent immobile was correlated with physician report of ECOG PS ($r=0.44$, $p=.004$). Patient-reported dyspnea on the FACT-L was associated with three assessments of physical functioning: physician report of ECOG PS ($r=-0.52$, $p<.001$); patient-reported walking speed ($r=-0.51$, $p=.001$); and percent of time awake and spent immobile ($r=-0.36$, $p=.02$). Based on our findings, we will use actigraphy as an objective measure of physical activity in the current study.

Summary of Preliminary Studies: For the past decade, our team has successfully collaborated on numerous supportive care studies for patients with lung and other cancers. The above studies highlight our accomplishments in demonstrating the need to treat dyspnea; developing and testing behavioral interventions in cancer; implementing nurse-administered symptom management trials; and using novel technologies for assessment.

Innovation of Proposed Study

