2.0 OBJECTIVES

2.1 Primary Aim

To demonstrate the efficacy of the brief behavioral intervention for improving self-reported dyspnea (primary outcome) in patients with advanced lung cancer

Hypothesis: Participants with advanced lung cancer who are randomly assigned to receive the brief behavioral intervention will report statistically and clinically significant improvements in dyspnea compared to those assigned to usual care.

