6.0 STATISTICAL ANALYSIS

6.1 Study Endpoints

6.1.1 Primary and Secondary Endpoints

The primary outcome is comparison of the MMRCDS and CDS severity scores at 8-week post-assessment between study arms, controlling for baseline values.

The secondary outcomes will be comparison of quality of life, anxiety, depression, and activity level between study groups. To assess quality of life, we will compare the post-assessment (8-week) FACT-L scores between study arms, controlling for baseline values. To evaluate anxiety and depression symptoms, we will similarly compare the continuous scores as well as rates of depression and anxiety symptoms reported per HADS score at 8 weeks between study arms, controlling for baseline values. To assess activity level, we will compare the percentage of time spent immobile but awake on actigraphy and self-report weekly leisure-time physical activity score at 8 weeks between study groups, controlling for baseline values.

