Aim 2: To demonstrate the efficacy of the brief behavioral intervention for improving quality of life, anxiety, depression, and activity level (secondary outcomes) in patients with advanced lung cancer.

Hypothesis 2: Participants with advanced lung cancer who are randomly assigned to receive the brief behavioral intervention will experience statistically and clinically significant improvements in quality of life (FACT-L), anxiety and depression (HADS), as well as activity level (per self-report Godin-Shephard Leisure-Time Physical Activity Questionnaire and the percentage of time spent immobile but awake on actigraphy) compared to those assigned to usual care.

Analyses: The statistical significance of between-group differences for the continuous secondary outcomes will be assessed with general linear models (GLM) and linear mixed models, with appropriate covariates and an alpha level of .05. We will examine the between-group differences (i.e., intervention versus control) at 8-week post-assessment for each specific secondary outcome (all are continuous variables), controlling for baseline values. In the event that the effect of the intervention differs by cancer type, use of opiate medication or other patient characteristic, we will examine these variables as interaction terms in the GLM analysis. We will explore independent improvements in these secondary outcomes by adding changes in MMRCDS or CDS severity scores as a covariate. Finally, we will also again estimate practical and clinical significance of these outcomes (using Cohen's d and Reliability Change Index) and conduct linear mixed models to examine the trajectory of between-group differences in these variables across all study time points.

6.3.3 Aim 3

Aim 3: To explore mediators and moderators of the effect of the brief behavioral intervention on patient-reported outcomes.

Hypothesis 3: Intervention effects on patient-reported dyspnea will be mediated by improved mastery in managing breathlessness and potentially moderated by patient demographic and clinical factors (e.g., gender, age, opioid use, performance status, and disease comorbidity).

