Analyses: We will conduct bootstrapped tests of mediation to determine whether group differences in self-reported dyspnea (outcomes: MMRCDS and CDS) are mediated by improved mastery in managing the symptom (mediator: CRQ). Finally, we will create interaction terms for the GEE analyses and linear mixed models to examine whether differences in reported dyspnea are moderated by patient factors (e.g., gender, age, opioid use, etc.).

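### Adjusting secondary outcomes for change in dyspnea does not isolate an independent benefit unless assumptions hold that the plan does not state and its own model makes doubtful

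*Combined protocol and SAP*

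**What the plan says.** For Aim 2 (section 6.3.2) the main analysis is a baseline-adjusted comparison: "We will examine the between-group differences (i.e., intervention versus control) at 8-week post-assessment for each specific secondary outcome". Dyspnea change is not a term in it. The same paragraph then adds: "We will explore independent improvements in these secondary outcomes by adding changes in MMRCDS or CDS severity scores as a covariate".

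The added covariate is what the trial sets out to change. Section 2.1 gives the primary aim as "To demonstrate the efficacy of the brief behavioral intervention for improving self-reported dyspnea (primary outcome) in patients with advanced lung cancer", and section 6.1.1 says "The primary outcome is comparison of the MMRCDS and CDS severity scores at 8-week post-assessment between study arms, controlling for baseline values".

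The plan does not define what an independent improvement is as an estimand. It does not say whether MMRCDS or CDS will be used, does not list the covariates for this model, and gives no caution on interpretation.

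Section 6.3.3 plans a separate analysis: "We will conduct bootstrapped tests of mediation", to see whether group differences in dyspnea "are mediated by improved mastery in managing the symptom (mediator: CRQ"). There dyspnea is the outcome and mastery is the mediator.

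**The concern.** Once a variable affected by treatment enters the model, randomization no longer protects the arm coefficient. Three features of this protocol make that more than a formality.

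- **Shared causes.** Section 1.2 reports that "dyspnea is related to depression, anxiety, fatigue, cough, and decreased coping capacity in patients with cancer receiving palliative care services". Section 6.3.1 names disease progression as a factor to control for in the Aim 1 longitudinal models, but section 6.3.2 does not name it for this one.
- **Reverse causes.** The theoretical model in section 1.2 has physical, cognitive and behavioral responses acting on one another in both directions. Section 5.3.2 describes stress responses as feeding back into breathlessness. Distress, a secondary outcome, is therefore also a presumed cause of the covariate, and both are self-reported at the same visit.
- **Overlap and measurement error.** The actigraphy pilot in section 1.2 states "Patient-reported dyspnea on the FACT-L was associated with three assessments of physical functioning", so FACT-L carries its own dyspnea rating. MMRCDS is a single item with five grades.

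At stake is a statement that the intervention does, or does not, help quality of life, mood or activity beyond its effect on breathlessness. The planned model cannot support either statement on its own.

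**Working it through.** **1. The plan's own figure.** Section 6.2 gives 80% power for 200 completers, a difference of 0.40 SD and two-sided alpha 0.05. With 100 per arm, 0.40/√(2/100) = 2.83, and power is Φ(2.83 − 1.96) = 80.7% (80.4% with the t distribution). The figure reproduces, and this point does not alter it.

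**2. Model.** Let T be arm, M improvement in dyspnea (within-arm variance 1), Y a secondary outcome scored so that higher is better, and U an unmeasured common cause.

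- M = aT + √ρ·U + error
- Y = cT + bM + √ρ·U + error

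Here c is the true direct effect, and ρ is the within-arm correlation of M and Y that U induces when b = 0.

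- Without M, the arm coefficient is c + ab, the total effect.
- With M, the slope on M is b + ρ, so the arm coefficient is c + ab − a(b + ρ) = c − aρ.
- If M is observed with reliability r, the slope shrinks to r(b + ρ), and the arm coefficient is c + ab − a·r·(b + ρ).

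**3. Inputs.** From section 6.2: a = 0.40 (design difference), with 1.0 (pilot effect) as an upper end. Set c = 0, so that any non-zero result is error. The documents give no value for ρ, b or r. Assumed: ρ from 0 to 0.5, b = 0.4 (0.3 to 0.5 checked), r = 1 or 0.7.

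**4. Results for a = 0.40, c = 0, 200 patients.** Bias is from the formulas; rejection rates are simulated.

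| ρ | Bias, r = 1: −0.40ρ | Rejection | Bias, r = 0.7: 0.16 − 0.28(0.4 + ρ) | Rejection |
|---|---|---|---|---|
| 0 | 0 | 5% | +0.048 | 6% |
| 0.1 | −0.04 | 5-6% | +0.020 | 5% |
| 0.2 | −0.08 | 8-9% | −0.008 | 5% |
| 0.3 | −0.12 | 14% | −0.036 | 5% |
| 0.5 | −0.20 | about 36% | −0.092 | 9% |

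Repeat runs put the last r = 1 rejection rate between 34% and 38%, and the last r = 0.7 rate at 9-10%. With measurement noise alone (ρ = 0), bias is ab(1 − r) = 0.40 × b × 0.3: +0.036, +0.048 and +0.060 SD for b = 0.3, 0.4 and 0.5.

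At a = 1.0 and r = 1, bias is −0.10 to −0.50 SD over ρ = 0.1 to 0.5, with rejection from about 10% to 95%.

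The model without M recovered the total effect in every setting (for example 0.4 × 0.5 = 0.20 SD for b = 0.5). Adding U to the model with M restored about 5% rejection.

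**5. Direction.** Counting only significant results in favor of the intervention (nominal 2.5%): with r = 1 the rate is 0.2% at ρ = 0.3 and 0.0% at ρ = 0.5; with r = 0.7 it is 1.6% and 0.6%. Only noise with no shared cause raises it clearly, to 5.1%.

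**6. Reverse path.** Suppose mood improves by a genuine 0.40 SD and mood affects dyspnea with an assumed slope of 0.3, on top of a 0.40 SD effect of the intervention on dyspnea. The arm effect on M is 0.40 + 0.3 × 0.40 = 0.52. Adjusting for M gives 0.40 − 0.3 × 0.52 = 0.244 SD. Simulated detection falls from 80% to 41%.

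**The case against.** The strongest defense is that nothing confirmatory depends on this model. Section 6.3.2 words it as exploration, added to a week-8 comparison that has no such term. That stands: a reader might infer that the secondary results as a whole are compromised, and the documents do not support this.

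A reader might also infer that the adjusted coefficient is always biased. It is not. With no shared cause, no reverse path and a well-measured covariate, it recovers the direct effect. The defect is reliance on conditions that the plan neither states nor supports.

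A third tempting reading is that the analysis would manufacture independent benefits. Step 5 shows that positive shared causes push the other way. Only measurement noise acting alone inflates false benefit, and modestly.

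The supporting arguments have limits. CDS has twelve items, so the single-item criticism applies to MMRCDS only. The FACT-L overlap concerns one part of a 35-item instrument and does not touch HADS, the activity questionnaire or actigraphy. Disease progression is collected (section 5.4.2) and could fall under the unlisted covariates. The two error sources also partly offset each other, as the r = 0.7 columns show.

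The exploratory label does not settle the matter. It lowers the weight of the evidence, but it does not make the model estimate what it is said to explore.

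**Conclusion.** The point holds in a limited form. The main secondary comparison at week 8 is sound on this score. The add-on model conditions on the trial's own primary outcome, and its arm coefficient can be read as a direct effect only under three unstated conditions, which the protocol's links of dyspnea to mood and coping and its two-way theoretical model make doubtful.

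For a 0.40 SD dyspnea effect and no direct effect, the error runs from −0.04 to −0.20 SD if the covariate is measured perfectly, and from about +0.02 to −0.09 SD at reliability 0.7, over assumed shared-cause correlations of 0.1 to 0.5. With noise alone it is about +0.04 to +0.06 SD. The likelier mistake is to miss a direct benefit or to report apparent harm. These sizes rest on assumed correlations, slopes and reliability; only the 0.40 and 1.0 SD dyspnea effects come from the documents.

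This should be corrected, but it does not threaten the trial's main conclusions.

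**What to change.** State in section 6.3.2 that all inference on secondary outcomes rests on the model without dyspnea change. Then do one of two things.

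- **Delete** the sentence on adding dyspnea change.
- **Replace** it with a new exploratory mediation analysis. A reader might assume that Aim 3 already covers this, but its mediator is CRQ mastery and its outcome is dyspnea. The new analysis needs a named direct-effect estimand; a stated choice of MMRCDS or CDS; adjustment for baseline dyspnea, baseline outcome and the randomization strata (cancer type and site, section 4.3); and week-8 dyspnea as mediator of the week-16 or week-24 outcome where that is collected. Actigraphy stops at week 8 (section 5.4.1), so the later-outcome version cannot be done for it. Ordinary regression mediation conditions on follow-up dyspnea just as the present sentence does, and bootstrapping does not remove confounding. A sensitivity analysis for unmeasured mediator-outcome confounding and for measurement error is therefore part of the replacement.

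In either case, claim neither independent benefit nor its absence from the covariate-adjusted model alone.

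Cost: SAP wording and a little more analysis work. The variables named here are already collected.

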6.3.4 Exploratory Analyses of Service Utilization

Although we likely will not have sufficient power to examine statistically the intervention effects on service utilization, we will at a minimum calculate descriptive statistics on

rates of ED visits and hospitalizations by study group. Otherwise, if possible, we will conduct Fisher's exact tests and logistic regression to explore differences in rates of ED visits and hospitalizations between groups, controlling for any confounders as needed.

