5.4.2 Data from the Electronic Health Record

Clinical information regarding tumor type (NSCLC, SCLC, mesothelioma), date of diagnosis of advanced disease, previous cancer therapies, current treatment regimen, and performance status will be collected at baseline. The post study review of the electronic health record (EHR) will include information on disease progression, any changes in cancer treatment, and number of emergency department (ED) visits and hospitalizations during the study period.

Medical comorbidity will be assessed at the time of baseline data collection with the Charlson Comorbidity Index (CCI).⁶⁷ We will review health records for the presence of (1) pulmonary, cardiac, hepatic, and renal disease, (2) current and other malignancies, and (3) other morbidities (diabetes, cerebrovascular disease, and rheumatologic conditions) and assign the appropriate CCI score.

Medical orders: We will collect data on medications to alleviate dyspnea (e.g., opioid analgesics), supplemental oxygen, and procedures for managing pleural effusions or bronchial obstruction.

[name] (Co-I), a thoracic oncologist, will oversee the collection of clinical information from the EHR as well as the review of medical scans to determine whether participants'

disease progressed during the study period.

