5.5 Description of Study Processes

The following tables provide an overview of the study timeline and the timing of recruitment, enrollment, and participant contact.

Time Point	Study Procedure
Months 0-3	
Study Staff Training:
 
• Hire and train oncology nurses in content and delivery of the brief behavioral intervention for dyspnea• Hire and train 2 research assistants in study procedures, recruitment, enrollment, data collection, etc.

Months 4-54	
Randomized Controlled Trial:
 
 • Enroll and randomly assign 220 patients (110 per study group) to receive either the brief behavioral intervention for dyspnea or usual care across study sites (i.e., MGH Cancer Center, DFCI, Mass General Cancer Center at Newton-Wellesley Hospital, and Mass General/North Shore Cancer Center-Danvers) • Complete 8,16, 24-week post assessments and data extraction from the electronic health record
Months 55-60	
Analysis and Submission of Follow-up Grant Proposal:
 
 • Complete data analyses and submit primary manuscripts • Prepare and submit grant proposal for large-scale multisite dissemination and implementation study

Point of Contact	Timing	Study Procedures
Initial screen and consent	Upon clinician approval	
 ▪ Screen in outpatient clinic, infusion suite or via telephone ▪ Patients will self-report shortness of breath (using the MMRCDS) ▪ If MMRCDS score ≥ 2, study staff will obtain informed consent and email oncology clinician to notify that the patient screened positive for dyspnea ▪ If MMRCDS score < 2, study staff will screen patient again in 3 months
Enrollment - Baseline self-report assessment Randomization notification	Upon confirmation of prescreen eligibility	
 ▪ Participant completes self-report battery of questionnaires ▪ Provide patient with wrist actigraph and activity log with instructions to wear for the 3 days following the baseline assessment. ▪ After 3 days, study staff calls and informs patient of randomization and schedules session one for intervention participants. ▪ Participant returns actigraph watch and activity log in-person or mails it back to study staff.

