5.5.1 Instrument Administration

A study staff member blind to group assignment will administer study assessments at baseline and multiple follow-up time points (at weeks 8, 16, and 24) with a +/- 2 week window to accommodate patient schedules. The assessment battery takes approximately 30 minutes to complete. The baseline and follow up assessments (at 8, 16, and 24 weeks) will occur either in clinic, by mail, telephone or online via REDCap. We selected the six-month time frame for follow-up assessment to evaluate the long-term impact of the intervention on patient outcomes while recognizing the limited life expectancy of patients with advanced lung cancer. The self-report measures have strong psychometric properties and been well validated in previous studies.

If a participant expresses that he or she is not willing or able to complete the self-report packet in full, the study staff will offer an abbreviated version containing the primary outcome assessments (MMRCDS, CDS, HADS, and FACT-L). This short form will only be offered if a patient initially refuses to complete the entire questionnaire packet. Each participant will receive the actigraph at enrollment and will be instructed to wear the watch for the 3 days following their baseline assessment. In preparation for Week 8 follow-up, participants will receive the wrist actigraph either in person in clinic or by mail.

Patients will be instructed to wear the actigraph device for the 3 days following the completion of their 8-week self-report assessment. After this 3-day period, study staff will arrange a FedEx pick-up to retrieve the actigraph device.

If a patient passes away while in possession of an actigraph, we will call the person identified as a contact in the Participant Locator Form to offer our condolences. We will also explain that we will send a prepaid envelope to them addressed to our study staff, and instruct them to place the actigraph in the envelope, seal it, and send the envelope back to us in the mail (USPS). If we cannot reach the patient's contact by phone, we will send the prepaid envelope along with a note offering our condolences and instructions on how to return the actigraph.

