5.6 Adverse Reactions and Their Management

5.6.1 Reporting Adverse or Unanticipated Events

Identification of adverse events may come through notification from the study participant, caregiver, clinician, or from review of the electronic health record. In such circumstances, the PIs and investigative team will follow the following procedures:

- a. Serious Adverse Events. Given that this study is a randomized trial comparing a brief behavioral intervention compared to a usual care control group, we do not anticipate any study-related events meeting the FDA definition of a SAE (i.e., any fatal event, immediately life-threatening event, permanently or substantially disabling event, event requiring or prolonging inpatient hospitalization, or any congenital anomaly). The proposed study population is comprised of individuals diagnosed with advanced lung cancer who frequently experience disease worsening, high rate of symptoms, and hospitalizations from the underlying disease and/or side effects of treatment. Therefore, as advanced lung cancer is a chronic-type terminal illness, regular fluctuations in cancer-related symptoms, disease worsening, hospitalizations, emergency department visits, and deaths are to be expected throughout the study, and we will not consider or report such events as SAEs in this trial.
- b. Non-Serious Adverse Events. The IRB will be provided with unblinded summaries of study related non-serious adverse events by treatment group at the continuing reviews. These reports will include types of events, severity, and treatment phase. To date, the majority of non-serious adverse events in our prior supportive care studies have been due to patient discomfort with the study questionnaires.

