6.3 Analysis Plan

6.3.1 Aim 1

Aim 1: To demonstrate the efficacy of the brief behavioral intervention for improving dyspnea (primary outcome) in patients with advanced lung cancer.

Hypothesis 1: Participants with advanced lung cancer who are randomly assigned to receive the brief behavioral intervention will report statistically and clinically significant improvements in dyspnea (per self-report MMRCDS and CDS) compared to those assigned to usual care.

Analysis: Analyses will begin with descriptive and graphical summaries of the endpoints. As the MMRCDS is an ordinal measure, the statistical significance of between-group differences in the primary outcome will be assessed first with the Wilcoxon-Rank Sum test and then with generalized estimating equations (GEE), with appropriate covariates. The CDS is a continuous interval measure, and we will assess between-group differences in these scores using general linear models (GLM). All statistical tests will be two-sided with an alpha level of .05. For these primary outcomes, we will examine between-group differences (i.e., intervention versus control) in MMRCDS and CDS scores at the 8-week post-assessment, controlling for baseline values. In the event that the effect of the intervention differs by cancer type, use of opiate medication or other patient characteristic, we will examine these variables as interaction terms in the GEE and GLM analyses. We will also evaluate generalized linear mixed models of the longitudinal data, allowing us to

account for dependency among MMRCDS and CDS scores over time and to control for demographic and clinical factors, such as disease progression, (as necessary for any imbalances in baseline variables) when examining between-group differences in the MMRCDS and CDS scores across the multiple study time points (i.e., baseline, 8, 16, 24 weeks). Finally, we will compute the effect sizes and Reliability Change Index⁶⁸ to assess practical and clinical significance of the differences in the primary and secondary outcomes. The GLM model will generate an effect size estimate, which can also be calculated by hand ($d = \text{Mean}_{\text{change score CBT group}} - \text{Mean}_{\text{change score control group}} / \text{SD}_{\text{pooled}}$). Cohen⁶⁹ utilizes cutoffs of 0.2 for a small effect, 0.5 a medium effect, and 0.8 for a large effect.

6.3.2 Aim 2

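### Section 6.3.4 reduces counts of ED visits and hospitalizations to any/none, losing power in a comparison the plan already calls underpowered; a count model should be added and read with deaths by arm.

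*Combined protocol and SAP*

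**What the plan says.** Section 5.4.2 has the post-study record review collect the "number of emergency department (ED) visits and hospitalizations during the study period". That is a count per patient.

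Section 6.3.4 commits to descriptive statistics by arm as a minimum and concedes that "we likely will not have sufficient power to examine statistically the intervention effects on service utilization". If feasible, it adds Fisher's "exact tests and logistic regression to explore differences in rates of ED visits and hospitalizations between groups", "controlling for any confounders as needed". It names no count model, person-time denominator or offset. It does not say how counts become yes/no, or how death during follow-up is handled for this endpoint.

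Observation time will vary between patients. Section 5.6.1 says that "hospitalizations, emergency department visits, and deaths are to be expected throughout the study", and section 5.5.1 follows patients for six months while acknowledging their limited life expectancy.

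**The concern.** The data are richer than the tests chosen for them. Any/none discards every visit after the first. That information is already collected, and it is lost in a comparison where the plan itself expects too little power. This loss needs no difference in survival between arms.

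A second issue arises only if mortality differs between arms. Any/none takes no account of time at risk: a patient who dies in week 4 without a visit counts the same as one observed visit-free for 24 weeks. Dividing by time alive looks like the remedy, but section 1.2 describes dyspnea worsening, and dyspnea-related ED use clustering, near the end of life. Under that pattern a rate per day alive can mislead in the other direction. At stake is how an exploratory utilization result would be read, not the trial's main conclusions.

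**Working it through.** **The plan's own power figure.** Section 6.2 gives 80% for 200 completers, 0.40 SD and two-sided 0.05. Check: 0.40 × √(100/2) = 2.828, and Φ(2.828 − 1.960) = 80.7% (80.4% with the t distribution). It reproduces, but it covers the primary and secondary outcomes only. No figure is given for utilization.

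**Inputs from the documents.** "Enroll and randomly assign 220 patients (110 per study group") in section 5.5; 24 weeks of follow-up; "All statistical tests will be two-sided with an alpha level of .05" in section 6.3.1.

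**Assumed inputs, not in the documents.** Control rate λ = 1 event per 24 weeks alive; negative binomial dispersion 1; rate ratio 0.65; 30% deaths by week 24 in each arm, with exponential death times.

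**Power of any/none, no deaths.** With dispersion 1, P(any event) = λ/(1 + λ).
- Control: 1/2 = 50.0%. Intervention: 0.65/1.65 = 39.4%.
- SE = √[(0.500 × 0.500 + 0.394 × 0.606)/110] = 0.0667.
- z = 0.106/0.0667 = 1.59; power ≈ Φ(1.59 − 1.96) = 36%.

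**Power of the count model, no deaths.** Var(log rate ratio) = (1/μ₀ + 1/μ₁ + 2 × dispersion)/110.
- (1 + 1/0.65 + 2)/110 = 0.0413; SE = 0.203.
- z = 0.431/0.203 = 2.12; power ≈ Φ(2.12 − 1.96) = 56%.

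**The same with 30% deaths per arm.** Hazard h = −ln 0.70 = 0.357 per 24 weeks, so mean time alive is 0.30/0.357 = 0.841 of follow-up.
- Any/none: P(any) = 0.70·λ/(1 + λ) + ∫₀¹ h·e^(−ht)·λt/(1 + λt) dt = 43.8% v 34.1%. SE 0.0654, z = 1.48, power 31%.
- Count model: μ₀ = 0.841, μ₁ = 0.547. SE = √[(1.189 + 1.829 + 2)/110] = 0.214, z = 2.02, power 52%.

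Simulation of this setting gives 32-35% for any/none against 50-58% for the count model, with or without a rise in events before death.

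**Sensitivity.** At rate ratio 0.6 and 25% deaths in each arm, over 0.5 to 1.5 events per 24 weeks and dispersion 0.5 to 2, simulated power is 24-50% (Fisher), 28-55% (logistic) and 40-85% (negative binomial with offset).

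**Unequal mortality, no true rate difference, constant event rates.** At 40% v 20% deaths, simulated P(any event) is 41.7% v 46.1%, so the arm with more deaths looks better.
- SE = √[(0.417 × 0.583 + 0.461 × 0.539)/110] = 0.0669; z = 0.044/0.0669 = 0.66; rejection probability about 10%.
- The simulated type I error of the logistic test is 9-11%, against 5-6% for a person-time model. At 30% v 20% deaths the logistic figure is about 6-7%, which is negligible.

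**Unequal mortality, events rising before death.** Assume the rate is 5 times higher in the last 4 weeks of life. Each death then adds about (5 − 1) × 4/24 = 0.667 expected events, ignoring deaths in the first 4 weeks. Mean time alive is 0.783 (40% deaths) and 0.896 (20% deaths).
- Expected events: 0.783 + 0.40 × 0.667 = 1.050 v 0.896 + 0.20 × 0.667 = 1.030.
- Per unit of time alive: 1.050/0.783 = 1.341 v 1.030/0.896 = 1.149, a spurious rate ratio of 1.17 against the arm with more deaths.
- SE = √[(1/1.050 + 1/1.030 + 2)/110] = 0.189; z = 0.154/0.189 = 0.82; rejection probability about 13%.
- Simulated type I error of the offset model is 12% at a 5-fold rise and 21% at 8-fold, against 5-6% for any/none.
- Without the offset, the expected count ratio is 1.050/1.030 = 1.02 here, but 0.783/0.896 = 0.87 when event rates are constant. Fitting the model both ways therefore shows how far the result depends on this assumption.

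**The case against.** The strongest case for leaving the text alone has four parts.

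- **'Rates' may simply mean proportions.** Section 6.1.1 speaks of rates of HADS-defined anxiety and depression, and section 6.2 of an attrition rate; both are proportions. On that reading Fisher's test and logistic regression suit the estimand, and collecting counts does not oblige anyone to model them. This stands. A reader might infer that section 6.3.4 contradicts itself; the documents do not support that.
- **The bias argument cuts both ways.** A reader might infer that the planned tests are biased by death and that a person-time model cures this. The documents do not support that either. Any/none is distorted only if mortality differs materially between arms and event rates do not climb before death. The protocol hypothesizes no survival effect. The survival benefit cited in section 1.2 belongs to a far more intensive multi-specialist program. Section 1.2 also points to end-of-life clustering of ED use, under which the offset model is the one that errs. The direction comes from the protocol; the 5- to 8-fold size is an assumption.
- **The analysis is exploratory and conditional.** This limits the weight of the point. It is not a reason to prefer the weaker test when the counts are in hand.
- **The confounder clause could admit follow-up time.** It could, but it does not name it, and no covariate restores counts already collapsed to any/none.

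**Conclusion.** The point holds as one of efficiency. Under the stated assumptions, any/none has about 32-35% power where a count model has 50-58%. The gain persists across the other rates and dispersions tried, though its size depends on inputs the documents do not give. At 50-58% the comparison is still not well powered, so a null result would remain inconclusive.

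It does not hold as a finding that the planned tests are biased, or that an offset model is the safer choice whenever deaths differ. At 40% v 20% deaths, any/none favours the arm with more deaths when event rates are constant (type I error about 10%). The offset model penalises that arm when utilization rises before death (about 12-21% at a 5- to 8-fold rise in the last 4 weeks). Neither can be read without deaths by arm.

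This is a minor improvement to an exploratory analysis. Primary and secondary conclusions are untouched.

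**What to change.** In section 6.3.4:

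- Add, as the main exploratory comparison, a negative binomial (or Poisson with robust variance) model of the counts in all randomized patients, so that the completers-first approach of section 6.4 does not drop patients who die. Adjust for the randomization strata in section 4.3, pooling sparse cancer types if needed. Use log days alive and under observation as offset.
- Fit the same model without the offset as a sensitivity analysis.
- Keep the any/none Fisher and logistic comparison alongside.
- Report deaths by arm next to these results, and state that if mortality differs, none of the estimates can be taken as unbiased on its own.
- Define the study period over which events and days are counted, including for intervention patients whose baseline is reset under section 5.5.2.

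The cost is SAP wording and some programming, with no new patients, visits or assessments. Section 5.4.2 does not list date of death or last follow-up among the items abstracted, so the chart review must be confirmed to capture it. The statistical downside is the offset model's sensitivity to a rise in utilization before death. That is why the version without the offset and the any/none results stay in the report.
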